11.6.5 Columbia Suicide Severity Rating Scale

The C-SSRS will be performed according to the Schedule of Assessments (Table 3-2).

11.6.6 Contraception and Pregnancy

11.6.6.1 Contraception

Following the recommendations outlined by the Heads of Medicines Agencies Clinical Trial Facilitation Group, study participation requires a commitment from the subject that he/she and his/her partner use **1 acceptable method of contraception** that is listed in Table 11-2 from the Screening Visit through 90 days after the last dose of study drug. Male subjects must also not donate sperm from the first study drug dose through 90 days after the last dose of study drug. Additional contraception requirements may need to be followed according to local regulations and/or requirements.

The contraception requirement for the couple is waived for the following:

- True abstinence for the subject, when this is consistent with the preferred and usual lifestyle of the subject. True abstinence must be practiced from the Screening Visit through 90 days after the last dose of study drug. Periodic abstinence (e.g., calendar, ovulation, symptothermal, postovulation methods) and withdrawal are not acceptable methods of contraception.
- If the male is infertile (e.g., bilateral orchiectomy). Infertility may be documented through examination of a semen specimen.
- If the female is of non-childbearing potential. To be considered of non-childbearing potential, the female must meet at least 1 of the following criteria:
 - o Postmenopausal: Amenorrheic for at least 2 years and a serum follicle-stimulating hormone level within the laboratory's reference range for postmenopausal females
 - o Documented bilateral oophorectomy and/or hysterectomy
- Same sex relationships

Unique situations that may not fall within the above specifications may be discussed with the sponsor's medical monitor or designee on an individual basis.

Table 11-2 Acceptable Methods of Contraception

Contraceptive Method	Male Subjects and Their Female Partners	Female Subjects and Their Male Partners
Documented vasectomy (with a negative sperm postvasectomy semen analysis) at least 6 months before the first dose of study drug	Yes	Yes
Condom with spermicide (either as a single product if commercially available and/or allowed according to local regulations; otherwise condom and spermicide as separate products) used alone or in combination with cap, diaphragm, or sponge with spermicide	Yes ^a	Yes ^a
Documented bilateral tubal ligation performed at least 6 months before the first dose of study drug	Yes	Yes
Continuous use of an intrauterine device (non-hormone releasing) for at least 90 days before the first dose of study drug	Yes	Yes
Hormonal contraceptives, if successfully used for at least 60 days before the first dose of study drug	Yes	No ^b

^a Female condom cannot be used with male condom due to risk of tearing.

11.6.6.2 Pregnancy

Subjects will be counseled to inform the investigator of any pregnancy that occurs during study treatment and for 90 days after the last dose of study drug.

If a subject or the female partner of a male subject becomes pregnant while participating in the study, study drug will be permanently discontinued immediately. The investigator will notify the medical monitor and Vertex GPS within 24 hours of the site's knowledge of the subject's (or partner's) pregnancy using the Pregnancy Safety Information Collection Form.

If confirmed to be on active drug, the subject or partner will be followed for safety (adverse events) until the end of the pregnancy and similarly, the infant will be followed for 1 year after the birth, provided informed consent is obtained. A separate ICF will be provided to explain these follow-up activities. Pregnancy itself does not constitute an AE.

12.1 Sample Size and Power

The primary efficacy endpoint is the change from baseline in the weekly average of daily pain intensity on the 11-point NRS, as reported in the daily diary, at Week 6. The primary analysis of the primary efficacy endpoint will be a within-group treatment comparison in the VX-150 treatment group. The 95% CI for the within-group change will be used to evaluate if there is any significant change from baseline (within-group change against 0). Additional analyses will include an evaluation of this within-group change against 0.8, an expected change from the placebo group, and a 95% CI for the between-group comparison of change from baseline.

Assuming a within-group change of 0.8 for placebo and a between-group treatment difference of 1.25²²⁻²⁴, the expected within-group change for VX-150 is 2.05. With an SD of 2.08, the power for the 95% CI for the within-group change to rule out 0 or 0.8 is summarized in Table 12-1 for 25, 35, or 45 evaluable subjects per group. The power for the 95% CI for the between-group treatment difference to rule out 0 is also provided. In order to allow for withdrawal of up to 20% of randomized subjects over 6 weeks of treatment, the study will enroll and randomize a minimum of approximately 62 subjects (25 evaluable subjects per group) and up to approximately 114 subjects (45 evaluable subjects per group) in total.

Table 12-1 Power for the 95% CIs for Within- and Between-group Changes

Number of Evaluable Subjects Per Group	Power for the 95% CI for the Within-group Change to Rule Out 0	Power for the 95% CI for the Within-group Change to Rule Out 0.8	Power for the 95% CI for the Between-group Treatment Difference to Rule Out 0
25	>99%	82%	55%
35	>99%	93%	70%
45	>99%	98%	81%

CI: confidence interval

12.2 Analysis Sets

Assignment of subjects to analysis sets will be performed before the clinical data lock for the study.

The All Subjects Set is defined as all subjects who have been randomized or have received at least 1 dose of study drug. This analysis set will be used in subject listings and disposition summary table, unless otherwise specified.

The Full Analysis Set (FAS) is defined as all randomized subjects who have received at least 1 dose of study drug. The FAS is to be used in efficacy analyses in which subjects will be analyzed according to their randomized treatment group and not to the treatment they actually received.

The Safety Set is defined as all subjects who have received at least 1 dose of study drug. The Safety Set is to be used for all safety analyses in which subjects will be analyzed according to the treatment they received and not according to their randomized treatment group.

The PK Set is defined as all subjects who have received at least 1 dose of study drug and for whom the primary PK data is considered to be sufficient and interpretable.

12.3 Statistical Analysis

The primary objective of this study is to evaluate the efficacy of VX-150 in treating pain caused by small fiber neuropathy.

This section presents a summary of the planned statistical analyses of efficacy and safety. The Vertex Biometrics department will analyze the data derived from this study. Statistical Analysis System Version 9.2 or higher will be used to generate all statistical outputs (tables, figures, listings, and data sets).

Statistical analysis and presentation details will be provided in the SAP.

12.3.1 General Considerations

All individual subject data for all individual subjects randomized or exposed to study drug will be presented in data listings. Continuous data will be summarized using the following descriptive summary statistics: the number of subjects (n), mean, SD, SE, median, minimum value (min), and maximum value (max). Categorical data will be summarized using counts and percentages.

Baseline value for the NRS daily diary scores and the DSIS will be defined as the average score from Day -7 to Day -1. For all other variables baseline will be defined as the most recent non-missing measurement collected before the initial administration of study drug.

12.3.2 Background Characteristics

12.3.2.1 Subject Disposition

The disposition summary will be based on the All Subjects Set.

The number and percentage of subjects in each of the following disposition categories will be summarized based on the FAS: completed treatment, prematurely discontinued the treatment and the reason for discontinuation, completed study (i.e., completed Safety Follow-up Visit), and prematurely discontinued study with a breakdown of the reasons for discontinuation.

12.3.2.2 Demographics and Baseline Characteristics

The following demographics and baseline characteristics will be summarized by treatment group based on the FAS: sex, age, race, ethnicity, weight, height, BMI, diagnosis of diabetes, and pain in the Run-in Period

No statistical tests will be carried out to evaluate any baseline imbalance between treatment groups.

12.3.2.3 Prior and Concomitant Medications

Medications taken 28 days before the Screening Visit and up to the Safety Follow-up Visit will be summarized by Preferred Name using the World Health Organization-Drug Dictionary Enhanced (WHO-DDE) for the FAS as frequency tables in 2 parts:

- 1. Prior medication: Medication that started before the first dose of study drug, regardless of when dosing of the medication ended.
- 2. Concomitant medication: Medication received at or after the first dose of study drug, medication that was received before initial dosing and continued after initial dosing of study drug, or medication with missing stop date.

Medication that started before the first dose of study drug and continued after the first dose of study drug will be summarized as prior medication and separately as concomitant medication. Medications with a missing start date will be considered to have a start date before the first dose of study drug.

12.3.2.4 Study Drug Exposure and Compliance

Exposure to study drug (i.e., duration of treatment) will be summarized for the FAS in terms of duration of treatment a subject received (in days), defined as the last day minus the first day of study drug plus 1.

Dosing compliance will be summarized for the FAS, and is calculated as the actual number of dosing occasions at which study drug was administered, as a percentage of the planned number of dosing occasions.

Duration of treatment and dosing compliance will be summarized by means of descriptive summary statistics.

12.3.3 Efficacy Analysis

Assessment of efficacy of VX-150 is the primary objective of this study. All efficacy endpoints will be analyzed based on the FAS.

12.3.3.1 Analysis of Primary Variable

The primary efficacy endpoint is the change from baseline in the weekly average of daily pain intensity on the 11-point NRS, as reported in the daily diary, at Week 6.

The primary analysis of the primary endpoint will be a within-group treatment comparison in the VX-150 treatment group. The analysis will be conducted using a mixed-effects model for repeated measures (MMRM). The between-group treatment comparison will also be generated using the same MMRM. The model will include the change from study baseline in the weekly average of daily pain intensity score as the dependent variable; treatment, sex, diagnosis of diabetes, week, and treatment-by-week interaction as fixed effects; subject as a random effect; and baseline pain intensity score as a covariate. In the model, week will be treated as a class variable, and an unstructured covariance matrix will be assumed to model the within-subject variability. The denominator degrees of freedom for the F-test for fixed effects will be estimated using the Kenward-Roger approximation.

The estimated mean and corresponding 95% CI for VX-150 will be provided for the withingroup change. The CI will first be used to facilitate the comparison with 0; this will be followed by a comparison with 0.8. In addition, the estimated mean and corresponding 95% CI for the between-group difference will be provided.

12.3.3.2 Analysis of Secondary Efficacy Variables

Secondary endpoints are:

• Proportion of subjects with ≥30% reduction in the weekly average of daily pain intensity on the 11-point NRS, as reported in the daily diary, at Week 6. This endpoint will be evaluated using descriptive statistics.

- Proportion of subjects with ≥50% reduction in the weekly average of daily pain intensity on the 11-point NRS, as reported in the daily diary, at Week 6. This endpoint will be evaluated using descriptive statistics.
- Change from baseline in the DSIS at Week 6. The analysis of this endpoint will be similar to the primary analysis.
- Proportion of subjects categorized as improved at Week 6 on the PGIC assessment. This endpoint will be evaluated using descriptive statistics.

• Change from baseline in pain intensity on the 11-point NRS, as reported at study visits, at Week 6. The analysis of this endpoint will be similar to the primary analysis.

12.3.4 Safety Analysis

The overall safety profile of VX-150 will be assessed in terms of the following safety and tolerability endpoints:

- Incidence of treatment-emergent adverse events (TEAEs)
- Clinical laboratory values (including coagulation studies)
- ECG outcomes
- Vital signs
- C-SSRS

Safety analyses will be based on the Safety Set.

All safety data will be presented in individual subject data listings.

12.3.4.1 Adverse Events

AEs will be coded according to MedDRA. The number and percentage of subjects experiencing an AE will be summarized by the MedDRA System Organ Class and Preferred Term, as well as by treatment group. AEs will be classified as pretreatment or treatment-emergent as follows:

Pretreatment AEs are defined as AEs that were reported or worsened after signing the ICF up to the start of study drug dosing.

Treatment-emergent AEs are defined as AEs that were reported or worsened on or after the start of study drug dosing through the Safety Follow-up Visit.

Only TEAEs will be summarized in tables. All summaries of TEAEs will be presented by the severity of the AE and relationship to the study drug. Some rules that will apply to the summarization of AEs are (1) a subject with multiple occurrences of the same AE or a continuing AE will only be counted once; (2) only the maximum severity level will be presented in the severity summary; and (3) only the worst relationship level will be presented in the relationship summary.

AEs leading to death, SAEs, AEs leading to dose discontinuation, and study discontinuation will be listed separately. All AEs through the Safety Follow-up Visit will be listed in an individual subject data listing, including pretreatment AEs.

12.3.4.2 Clinical Laboratory Assessments

All statistical analyses of laboratory values will be performed using SI units. Hematology (including coagulation) and clinical chemistry results will be summarized by treatment group at each scheduled time point. The number and percentage of subjects with at least 1 potentially clinically significant (PCS) event will be summarized by treatment group at each scheduled time point. A listing containing individual subject laboratory measurements meeting the PCS criteria will be provided. For each subject in the listing, laboratory measurements at all time points will be included. The PCS criteria for clinical laboratory data will be provided in the SAP. Urinalysis results will be listed only in individual subject data listings. These results will not be summarized. Clinically significant abnormal laboratory findings will be reported as AEs.

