9.4.2 Clinical Laboratory Assessments

All statistical analyses of laboratory values will be performed using International System of Units. The raw values and change from baseline values for the continuous hematology, clinical chemistry will be summarized by treatment group at each scheduled visit. The threshold value criteria for hematology and clinical chemistry laboratory tests are provided in [Appendix D](#). The number and percentage of subjects with at least 1 hematology and clinical chemistry laboratory measurement meeting the threshold value criteria will be summarized

by treatment group at each scheduled visit. Coagulation results will be summarized by treatment group at each scheduled visit. The number and percentage of subjects with abnormal coagulation values at each scheduled time point will be summarized.

A listing containing individual subject hematology and clinical chemistry laboratory measurements meeting the threshold value criteria at any visit will be provided. For each subject in the listing, laboratory measurements at all visits will be included. This listing will include data from scheduled and unscheduled time points. Abnormal coagulation and urinalysis results also will be listed separately. For each subject in the listing, coagulation and urinalysis results at all visits will be included. Results of the urine/serum pregnancy test will be presented in individual subject data listings only.

Clinically significant abnormal laboratory findings will be reported as AEs.

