9.4.3 Electrocardiogram

A summary of raw values and change from baseline values will be provided by treatment at each scheduled visit during the TE period for the following standard 12-lead ECG measurements: PR, QT, QRS, QTcF [QTcF = QT/RR^{0.33}], and HR. In addition, the number and percentage of subjects by maximum on-treatment value of QT/QTcF intervals, categorized as \leq 450 msec, $>$ 450 msec and \leq 480 msec, $>$ 480 msec and \leq 500 msec, and $>$ 500 msec, as well as maximum on-treatment change from baseline value of QT/QTcF intervals, categorized as \leq 0 msec, $>$ 0 and \leq 30 msec, $>$ 30 and \leq 60 msec, and $>$ 60 msec, will be provided.

The threshold value criteria for ECG data are provided in [Appendix D](#). A listing containing individual subject measurements meeting the threshold value criteria at any visit will be provided. For each subject in the listing, ECG measurements at all visits will be included.

Clinically significant ECG abnormalities occurring during the study through the Safety Follow-up Visit will be recorded as AEs.

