9.4.4 Vital Signs

The raw values and change from baseline values during the TE period will be summarized by treatment at each scheduled visit: systolic and diastolic blood pressure (mm Hg), body temperature (°C), pulse rate (beats per minute), and respiratory rate (breaths per minute).

The threshold value criteria for vital signs data are provided in [Appendix D](#). A listing containing individual subject measurements meeting the threshold value criteria at any visit will be provided. For each subject in the listing, vital signs at all visits will be included.

Clinically significant abnormal findings in vital signs will be reported as AEs.

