Appendix D: Threshold Value Criteria

Table 12-3 Threshold Value Criteria for Laboratory Tests

Parameter	Comments	
Clinical Chemistry		
ALT	$\leq 3 \times \text{ULN}$ * (Not a PCS criterion) $>3x$ to $\leq 5x\text{ULN}$ $>5x$ to $\leq 8x\text{ULN}$ $>3x\text{ULN}$ $>5x\text{ULN}$ $>8x\text{ULN}$	FDA DILI Guidance Jul 2009.
AST	$\leq 3 \times \text{ULN}$ * (Not a PCS criterion) $>3x$ to $\leq 5x\text{ULN}$ $>5x$ to $\leq 8x\text{ULN}$ $>3x\text{ULN}$ $>5x\text{ULN}$ $>8x\text{ULN}$	FDA DILI Guidance Jul 2009.
ALT or AST	ALT $>3x\text{ULN}$ or AST $>3x\text{ULN}$	Vertex LFT working group 2014. To be counted within the same treatment period.
Alkaline Phosphatase	$>1.5x\text{ULN}$	FDA DILI Guidance Jul 2009.
Total Bilirubin	$>1.5x$ to $\leq 2x\text{ULN}$ $>2x\text{ULN}$	FDA DILI Guidance Jul 2009.
ALT and Total Bilirubin	ALT $>3x\text{ULN}$ and TBILI $>2x\text{ULN}$	FDA DILI Guidance Jul 2009. To be counted within a same treatment period.
AST and Total Bilirubin	AST $>3x\text{ULN}$ and TBILI $>2x\text{ULN}$	FDA DILI Guidance Jul 2009. To be counted within a same treatment period.
(ALT or AST) and Total Bilirubin	(ALT $>3x\text{ULN}$ or AST $>3x\text{ULN}$) and TBILI $>2x\text{ULN}$	Vertex LFT working group 2014. To be counted within the same treatment period.
CK	$>3x$ to $\leq 10x\text{ULN}$ $>10x\text{ULN}$	FDA criteria Feb 2005. Am J Cardiol April 2006.
Creatinine	$\geq 150 \text{ }\mu\text{mol/L}$ (Adults) $\geq 30\%$ change from baseline $\geq 100\%$ change from baseline	Benichou C., 1994.
Blood Urea Nitrogen	$\geq 17 \text{ mmol/L}$	
Chloride	$<85 \text{ mmol/L}$ $>115 \text{ mmol/L}$	
Sodium	$\leq 129 \text{ mmol/L}$ $\geq 150 \text{ mmol/L}$	

Table 12-3 Threshold Value Criteria for Laboratory Tests

Parameter		Comments
Potassium	<3 mmol/L ≥5.5 mmol/L	FDA Feb 2005.
Glucose		
Hypoglycaemia	<2.2 mmol/L	CTCAE criteria.
Hyperglycaemia	>13.9 mmol/L (fasted)	CTCAE criteria.
Albumin	≤25 g/L	
Thyrotropin	< LLN > ULN	
Cholesterol	≥20% increase from baseline	D. M. Hegsted and Robert J. Nicolos, 1987 Demacker PN et al., 1982.
Triglycerides	≥20% absolute change from baseline	D. M. Hegsted and Robert J. Nicolos, 1987 Demacker PN et al., 1982.
Low-density lipoprotein-direct	≥20% increase from baseline	D. M. Hegsted and Robert J. Nicolos, 1987 Demacker PN et al., 1982.
High-density lipoprotein	≥ 20% decrease from baseline	D. M. Hegsted and Robert J. Nicolos, 1987 Demacker PN et al., 1982.
Hematology		

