WBC	<3.0 Giga/L (Non-Black); <2.0 Giga/L (Black) ≥16.0 Giga/L	Increase in WBC: not relevant. To be interpreted only if no differential count available.
Lymphocytes	>4.0 Giga/L	
Neutrophils	<1.5 Giga/L (Non-Black); <1.0 Giga/L (Black)	International Consensus meeting on drug-induced blood cytopenias, 1991. FDA criteria.
Monocytes	>0.7 Giga/L	
Basophils	>0.1 Giga/L	
Eosinophils	>0.5 Giga/L or >ULN (if ULN≥0.5 Giga/L)	Harrison- Principles of internal Medicine 17th Ed., 2008.
Hemoglobin	≤115 g/L (Male); ≤95 g/L (Female) ≥185 g/L (Male); ≥165 g/L (Female) Decrease from Baseline ≥20 g/L	Criteria based upon decrease from baseline are more relevant than based on absolute value. Other categories for decrease from baseline can be used (≥30 g/L, ≥40 g/L, ≥50 g/L).
RBC	≥6 Tera/L	
Platelets	<100 Giga/L ≥700 Giga/L	International Consensus meeting on drug-induced blood cytopenias, 1991.

Table 12-4 Threshold Value Criteria for ECGs

Parameter	Comments
HR	≤ 50 bpm and decrease from baseline ≥ 10 bpm ≥ 120 bpm and increase from baseline ≥ 10 bpm
PR	≥ 220 ms and increase from baseline ≥ 20 ms
QRS	≥ 120 ms
QTc	Absolute values (ms)
Borderline	Borderline: 431-450 ms (Male); 451-470 ms
Prolonged*	(Female)
Additional	Prolonged: >450 ms (Male); >470 ms (Female) ≥ 500 ms
	Increase from baseline
	Borderline: Increase from baseline 30-60 ms
	Prolonged: Increase from baseline >60 ms

Note: Based on CPMP 1997 guideline.

Table 12-5 Threshold Value Criteria for Vital Signs

Parameter	PCS	Comments
HR	≤ 50 bpm and decrease from baseline ≥ 20 bpm ≥ 120 bpm and increase from baseline ≥ 20 bpm	To be applied for all positions (including missing) except STANDING.
SBP	≤ 90 mmHg and decrease from baseline ≥ 20 mmHg ≥ 160 mmHg and increase from baseline ≥ 20 mmHg	To be applied for all positions (including missing) except STANDING.
DBP	≤ 45 mmHg and decrease from baseline ≥ 10 mmHg ≥ 110 mmHg and increase from baseline ≥ 10 mmHg	To be applied for all positions (including missing) except STANDING.
Weight	$\geq 5\%$ increase from baseline $\geq 5\%$ decrease from baseline	FDA criteria Feb 2007.

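### The by-arm laboratory threshold counts do not separate subjects already over an absolute limit at baseline, so new threshold crossings cannot be read by arm

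*Protocol*

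**What the plan says.** Protocol 12.3.4.2 plans this for every scheduled visit: "number and percentage of subjects with at least 1 potentially clinically significant (PCS) event will be summarized by treatment group". It leaves the criteria to the SAP. SAP 9.4.2 is the operative text: "The number and percentage of subjects with at least 1 hematology and clinical chemistry laboratory measurement meeting the threshold value criteria will be summarized", split by arm and scheduled visit. It adds a count of subjects with abnormal coagulation values at each time point. Neither section sets a condition on baseline status, and no laboratory shift table or treatment-emergent laboratory flag is planned.

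The laboratory thresholds in SAP Appendix D (Table 12-3) are of two kinds:

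- **Absolute limits:** for example ALT, AST, bilirubin, CK, glucose, thyrotropin outside its reference range, white cells and differential, and platelets.
- **Change from baseline:** cholesterol, triglycerides, LDL, HDL, and one or more of the criteria for creatinine and hemoglobin.

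In the hemoglobin row the SAP remarks: "Criteria based upon decrease from baseline are more relevant than based on absolute value".

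SAP Appendix A (Table 12-1) assigns pre-dose samples to Baseline. The first post-baseline laboratory window takes post-dose samples only.

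**The concern.** A subject who is over an absolute limit before dosing and is still over it at Week 3 or Week 6 is counted at those visits exactly like a subject who crossed the limit after starting treatment. The table therefore mixes persistent and new abnormality.

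Such subjects are plausible here. Up to about 60% of the sample may have diabetes, up to about 20% may have HbA1c from 8% to below 11%, and no exclusion removes a subject merely for exceeding a Table 12-3 limit. Randomisation is stratified by sex and diabetes, not by any laboratory value.

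Safety is a secondary objective, and these are the only by-arm counts of laboratory threshold crossings. If persistent cases are common for a parameter, a real effect looks smaller in relative terms, and chance imbalance at baseline carries into the post-dose comparison.

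**Working it through.** The documents state no threshold rate, prevalence or persistence, so there is no figure of the plan to reproduce. What follows is an illustration.

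**Inputs**

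- Arm size 57, from Protocol 12.1: 114 / 2 = 57, consistent with 45 / (1 − 0.20) = 56.25, rounded up.
- *b*, share of subjects meeting the criterion at baseline: assumed, 0% to 20%.
- *r*, share of those still meeting it after dosing: assumed 80%, equal in both arms.
- *p*, new-onset rate among subjects not meeting it at baseline: assumed 3% on placebo and 15% on VX-150.

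**Formula.** Displayed rate = *b·r* + (1 − *b*)·*p*. A count restricted to subjects at risk displays *p* itself, so it shows 3% against 15% (difference 12.0 points, ratio 5.0) at every *b*.

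**Planned count**

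| *b* | Placebo | VX-150 | Difference (points) | Ratio |
|---|---|---|---|---|
| 0% | 3.0% | 15.0% | 12.0 | 5.0 |
| 5% | 0.040 + 0.0285 = 6.85% | 0.040 + 0.1425 = 18.25% | 11.4 | 2.66 |
| 10% | 0.080 + 0.027 = 10.7% | 0.080 + 0.135 = 21.5% | 10.8 | 2.01 |
| 20% | 0.160 + 0.024 = 18.4% | 0.160 + 0.120 = 28.0% | 9.6 | 1.52 |

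At *b* = 10% this is about 6.1 against 12.3 subjects of 57. About 4.6 in each arm (0.08 × 57) were already abnormal before dosing.

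**Sensitivity.** With new onset of 2% against 10% (true ratio 5.0) and *b* = 10%:

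- *r* = 1: 11.8% against 19.0%, ratio 1.61.
- *r* = 0.5: 6.8% against 14.0%, ratio 2.06.
- In both cases the difference is 7.2 points in place of 8.0.

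The absolute difference shrinks only by the factor (1 − *b*). The ratio falls much more.

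**Chance baseline imbalance.** The SD of the between-arm difference in baseline prevalence is √(2*b*(1 − *b*)/57): 4.1, 5.6 and 7.5 points at *b* = 5%, 10% and 20%. The persistent part of any imbalance appears in the post-dose counts.

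No test of these counts is planned, so no power figure is given.

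**The case against.** Much of the case on the other side stands.

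- **Eligibility.** Exclusion 10 removes subjects whose abnormal laboratory results indicate significant disease, in the investigator's opinion. Exclusion 6 removes subjects with unstabilised diabetes, and Protocol 11.6.2 requires screening results free of clinically significant findings that preclude participation. A prevalence of 10% to 20% is therefore unsupported for limits such as ALT above three times the upper limit. These rules rest on judgement, however, and do not exclude everyone over a Table 12-3 limit.
- **Other outputs.** SAP 9.4.2 lists every flagged subject, and every subject with abnormal coagulation, with all visits shown. It summarises change from baseline for hematology and chemistry, and clinically significant worsening becomes an adverse event. With about 114 subjects, new cases can be found by hand. None of these gives a by-arm incidence of new crossings, and no change summary is stated for coagulation.

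Two stronger readings are tempting, and the documents do not support them.

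- A reader might infer that the plan reports pre-existing abnormality as an on-study event. The text does not call the counts new or treatment-emergent. They are by-visit counts, a pre-dose value alone never enters a post-baseline window, and Baseline is itself an analysis visit. Whether the threshold table will carry a Baseline row is not stated. Such a row would show prevalence by arm, but not which later cases are new.
- A reader might infer that the SAP contradicts itself, because its blood pressure criteria pair a limit with a change, as in "≥ 160 mmHg and increase from baseline ≥ 20 mmHg". Those vital-sign criteria, and the ECG criteria in the same appendix, feed listings and not by-arm counts. QRS and the absolute QTc limits carry no baseline condition either. The hemoglobin remark sits in hemoglobin's own row, where a decrease criterion already implements it.

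**Conclusion.** The point holds as a limitation of the planned display, not as an error in a stated figure. For the absolute limits in Table 12-3 and for abnormal coagulation, subjects with persistent pre-dose abnormality enter the post-dose by-arm counts, and nothing planned shows by arm how many crossings are new. Randomisation balances this in expectation, so the effect is dilution and added noise, not systematic bias towards one arm.

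The size depends wholly on assumed prevalence, persistence and onset. It is nil at zero prevalence. In the main illustration at 10% it turns a five-fold ratio into about two-fold while costing 1.2 points of a 12-point difference. It will vary by parameter and is likely to be small where baseline crossing is rare. This is a cheap improvement to the safety comparison.

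**What to change.** In SAP 9.4.2, for each absolute-limit criterion and for abnormal coagulation, add a by-arm count of subjects who meet it on a post-dose sample in the treatment-emergent period and did not meet it at baseline, or met only a lower category. Use the subjects at risk as the denominator. A shift table from baseline to worst post-dose category would serve equally well. Keep the planned all-subject counts by visit, and leave the change-from-baseline criteria as they are.

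The cost is one extra programmed table, with denominators that vary by parameter and so need a footnote. It uses data already collected. No protocol amendment is needed, because Protocol 12 and 12.3.4.2 leave the analysis details and the criteria to the SAP.
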